13.4.1.1 Attack Checklist

The following is the Attack Checklist:

Do this as soon as the aura symptoms start:

- 1. Unpack a study device
- 2. Move green slider to this setting: \Box
- 3. Unfold the device's bag and pull the black plastic strip
- 4. Click the top of the device into place at an angle
- 5. Put on the nose clip (not tight)
- 6. Inflate the bag with 2 to 3 breaths

³This prevents post-treatment hyperventilation symptoms (mainly paresthesias and lightheadedness) which otherwise may occur in approx. 10-15% of users.

7. Start breathing through the device while sitting comfortably

8. IMPORTANT: Open the study app with Touch ID or PIN: \Box , then go to My Forms and press "Attack Start".

- 9. Answer all questions in the app (scroll all the way down), then press "Save"
- 10. Breathe through the device until the aura symptoms are gone (minimum 10 min.)
- 11. Turn the slider to setting 1 and breathe through it for five minutes
- 12. Set a timer to remember to report symptoms in app 1, 2, 24 & 48h after "Attack Start"

NB: The \Box symbol in step 2 and 8 is an empty text box. This is filled out during the Instruction Session.

13.4.2 Stage 1 Telephone/Teleconference Follow-up Contacts

13.4.2.1 Follow-up A (obligatory)

When the participant has reported his/her training attack in the ePRO app, the PI must within one week check whether the data was entered correctly, and then contact the participant via phone or teleconference in order to correct any data entry method errors observed, verify that the participant understands the use of the device and ePRO app, and answer any questions the participant may have.

13.4.2.2 Follow-up B (conditional)

If the participant has not registered an attack in the pasteight weeks, the PI must within one week contact the participant via phone or teleconference, in order to verify that the participant understands the use of the device and ePRO app and answer any questions the participant may have.

13.4.2.3 Follow-up C (obligatory)

When participants have treated and reported four attacks, the PI must within one week contact the participant in order to schedule his/her Site Visit 2.

Participants who at the overall conclusion of Stage 1 have not reported at least one study attack will be concluded from Stage 1 and invited to participate in Stage 2.

13.5 Site Visit 2

At Site Visit 2, the participant answers additional general questions about Stage 1, and it is disclosed to the participant whether they have received the active or sham device in Stage 1. Participant is asked to re-consent to further participation in Stage 2. This will be documented in the eCRF form for Stage 2.

If the participant does not wish to continue, they at this point give back all study materials and their participation in the study is concluded. Devices are accounted for in accountability logs and filed in Investigational Site File and Trial Master File.

If the participant wishes, they at this point continue into Stage 2 in which case they receive a Stage 2 study kit including with five active devices and the Instructions for Use for the active device. PI trains the participant in study procedures for this stage, including use of the study device, as well as data and safety reporting.

Table 4: Tasks during Site Visit 2

TASKS	, Site Visit 2:
-	End-of-Stage-1 interview (subjective satisfaction, side effects, non-reported adverse events, DASS-21 questions, participant's belief about which device type they were assigned in Stage 1 (active/sham))
-	Disclosure to patient of study device type used in Stage 1
-	Return of unused devices from Stage 1
-	Information and training about Stage 2 (open-label extension). Participant receives Stage 2 study kit if he/she re-consents to participating in Stage 2.

13.6 Stage 2

During Stage 2, participants can use the study devices to treat migraine-with-aura attacks.

Once each month during Stage 2, the participant is prompted (by notification via the study diary app) to answer the Stage 2 questions regarding use of the study device as well as use of prescription acute migraine drug or an over-the-counter acute analgesic, with the intention to treat migraine (cf. **PAREMA1 Case Report Form content**). The study diary questionnaire includes an option for reporting problems and/or adverse events.

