10.3.3 Blinding

To ensure optimal blinding of participants, the active and sham devices have been designed to look and feel as similar as possible (see section 8.6).

11 Endpoints

For this study to be considered successful, all primary performance and safety endpoints must be achieved. Data for all endpoints will be collected through electronic Patient Reported Outcome (ePRO). All end points have been selected with the aim of measuring effects and factors that are relevant and valuable for migraine patients.

All primary and secondary effectiveness endpoints are calculated based on data from Stage 1 of the study.

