11.2 Primary safety endpoint

- Incidence of device- or treatment-related adverse events
- Incidence of device- or treatment-related serious adverse events (SAEs) and/or serious adverse device effects (SADE)

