14.1.2 Risks related to the sham device

The sham device has been altered so that participants breathe very low CO₂ concentrations when using it (cf. section 8.6 and Investigator's Brochure).

A series of technical tests with the sham device found that the inspired CO₂ percentage with the sham device was less than 0.1% and no clinically or statistically significant changes in ETCO2 occur during use.

There are therefore no known or suspected risks with the sham device.

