15.2.2 Causality assessment

All AEs must have their relationship to both the study device and study procedure assessed and categorized by the Principal Investigator who examines and evaluates the participant based on the temporal and/or biological relationship and his/her clinical judgment. During assessment, relevant core documents (e.g. CIP, IB and RM report) must be consulted. The Sponsor and the investigators will use the following definitions to assess the relationship of the serious adverse event to the investigational device, sham or the investigation procedure.

Not related: Relationship to the device, sham or procedures can be excluded when:

- the event has no temporal relationship with the use of the investigational device, or the procedures related to application of the investigational device;
- the serious adverse event does not follow a known response pattern to the medical device (if the response pattern is previously known) and is biologically implausible;
- the discontinuation of medical device application or the reduction of the level of activation/exposure - when clinically feasible - and reintroduction of its use (or increase of the level of activation/exposure), do not impact on the serious adverse event;
- the event involves a body-site or an organ that cannot be affected by the device or procedure;
- the serious adverse event can be attributed to another cause (e.g. an underlying or concurrent illness/ clinical condition, an effect of another device, drug, treatment or other risk factors);
- the event does not depend on a false result given by the investigational device used for diagnosis, when applicable;
- **Possible:** The relationship with the use of the investigational device or comparator, or the relationship with procedures, is weak but cannot be ruled out completely.

Alternative causes are also possible (e.g. an underlying or concurrent illness/ clinical condition or/and an effect of another device, drug or treatment). Cases where relatedness cannot be assessed, or no information has been obtained should also be classified as possible.

Probable: The relationship with the use of the investigational device or comparator, or the relationship with procedures, seems relevant and/or the event cannot be reasonably explained by another cause.

Causal The serious adverse event is associated with the investigational device, comparator **relationship:** or with procedures beyond reasonable doubt when:

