15.4 Adverse Event Reporting by Investigators

If any event is considered (possibly) related to the device, event is considered serious or event is device deficiency with SAE potential, it is the responsibility of the Investigator to report this event within **24 hours** of awareness. If event is not serious or not related to the device, the Investigator must complete recording in EDC within 7 days of having become aware of the adverse event.

Overview of all (S)AEs will be provided to involved ECs in annual reports.

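### Stage 1 adverse events first elicited at Site Visit 2, or still unrated then, can be rated for causality after the allocation is disclosed at that visit

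*Protocol*

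**What the plan says.** Protocol 11.2 makes "Incidence of device- or treatment-related adverse events" a primary safety endpoint, together with related serious events. The opening of section 11 says that for the study to succeed "all primary performance and safety endpoints must be achieved".

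On who rates, 15.2.2 states: "All AEs must have their relationship to both the study device and study procedure assessed and categorized by the Principal Investigator". It also tells the rater to consult the investigation plan, the Investigator's Brochure and the risk management report.

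On when events come to light, Table 4 in 13.5 lists as the first Site Visit 2 task an "End-of-Stage-1 interview (subjective satisfaction, side effects, non-reported adverse events, DASS-21 questions" and, within the same item, the participant's guess about their device. The next item is "Disclosure to patient of study device type used in Stage 1". The text of 13.5 says the same of this visit: "it is disclosed to the participant whether they have received the active or sham device in Stage 1". Section 13.8 adds that each participant's code is broken at the conclusion of Stage 1.

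On recording time, 15.4 gives 24 hours from awareness for events that are serious or possibly device-related. For other events "the Investigator must complete recording in EDC within 7 days of having become aware of the adverse event".

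Section 13.7 says investigators are blinded to the device that each participant will use or has used. Section 15.5 has the sponsor's Medical Advisor adjudicate relatedness as well, without saying whether the advisor is blinded. The SAP says nothing on the blinding of causality ratings.

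**The concern.** An adverse event enters the primary safety endpoint only if it is judged related, so the endpoint is partly a matter of opinion. The blind protects that opinion only while the rater does not know the arm. Site Visit 2 is where late-reported events surface and also where the allocation is revealed, and the plan fixes no order between rating and disclosure.

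Knowing the arm could matter because the reference material differs by arm. Section 14.1.1 lists breathlessness, nausea, dizziness and other effects for the active device. Section 14.1.2 concludes: "There are therefore no known or suspected risks with the sham device". Several causality criteria in 15.2.2 turn on whether the event fits a known response pattern. The same report of dizziness can therefore read differently once the arm is known, leaning towards related under active and away from it under sham. The between-arm table of related Stage 1 events is the whole comparative safety result, and a rating made after disclosure cannot be re-blinded.

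**Working it through.** No arithmetic applies. The claim concerns the order of procedures, so the check traces one event through the plan.

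1. **Elicitation.** A participant mentions a Stage 1 side effect for the first time in the Site Visit 2 interview (13.5, Table 4). Table 4 puts this before disclosure, and asking for the participant's guess about the device makes sense only before disclosure. Elicitation is therefore planned under blind. The items are unnumbered, and they order the questioning, not the rating.

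2. **Disclosure.** The allocation is revealed at the same visit (13.5, 13.8). The text names the participant as the person told. Three facts imply that the investigator also learns it: the code is broken, disclosure is a task at the site visit, and 13.5 has the investigator train the participant for Stage 2 at that visit.

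3. **Rating.** The investigator supplies causality for the record (15.2.2, 15.3). The clock in 15.4 starts at awareness, which here is the interview. Both the 24-hour and the 7-day windows run past the end of the visit, so a rating entered that evening or later that week complies with the plan and follows disclosure.

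4. **Any rule that would prevent this.** Sections 13.5, 13.7, 13.8, 15.2 to 15.5 and 16.6 of the protocol, and the whole SAP, contain no requirement to enter, sign or lock causality before the code is released.

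5. **Second rating.** The Medical Advisor's adjudication (15.5) would repair the gap if it were blinded and if the safety table used it. Neither is stated. The advisor also sits on the sponsor's advisory board.

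6. **Timing of the code break.** Sections 10.3.1 and 13.4 end a participant's Stage 1 after four treated attacks, which comes before Site Visit 2. Sections 10.3 and 19.8 tie the end of Stage 1 to Site Visit 2 itself. On the first reading, 13.8 would allow the code to be broken before the interview takes place.

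7. **Emergency unblinding.** Under 13.8 the investigator is unblinded and the participant is then called in for Site Visit 2, so that interview takes place with the arm known. This should be rare.

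8. **How many events are exposed.** Only Stage 1 events first mentioned at Site Visit 2, or still unrated then. The schedule of events lists adverse event reporting at Follow-ups A, B and C. Follow-up C precedes Site Visit 2 by at most two weeks. Participants must report events through the app at once (15.3), and a report triggers a site call within one business day (13.10.1). Section 14.1.1 gives upper bounds for some active-device effects, but no section says how many events escape these routes, or gives rates for sham.

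**The case against.** The strongest reply is that the plan already covers most of this. Events are collected throughout Stage 1 and normally rated while blinded. The interview is listed ahead of disclosure. A second assessor adjudicates. Section 15.2.2 reserves *not related* for cases where a link can be excluded and sends unassessable cases to *possible*, and 15.1 includes a comparator device in the definition of an adverse device effect. Those rules work against automatic dismissal of sham events. Related events are only tabulated (16.6), and the pass/fail criterion in 16.7 concerns effectiveness alone. The Safety Management Plan and the Case Report Form content, which are not among the documents, might contain a gating rule.

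Most of this stands and limits the weight of the point. It does not close the gap. The order in Table 4 does not bind the rating, the advisor's blinding is unstated, and the default to *possible* narrows the rater's discretion without removing it. A rule in another document would answer the point, but 13.5 and 13.8 point to none on rating before disclosure.

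A reader might infer more than the documents support:

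- That investigators will in fact downgrade sham events. The plan leaves room for this but does not show that it will happen.
- That events already rated will be revised once the arm is known. Section 15.3 speaks of documenting changes in severity, not in causality.
- That mild effects surface mainly at this visit. No section says so.
- That a formal randomised safety comparison is compromised. No test or between-arm criterion is planned.

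**Conclusion.** The point holds in a limited form. Following the plan to the letter allows causality of some Stage 1 events to be rated after disclosure, and the primary safety endpoint depends on that rating. The consequence is possible bias in the between-arm table of related Stage 1 events. There is no type I error at stake, and the two-hour effectiveness data, which participants report in the app during Stage 1, are not touched.

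The size cannot be estimated from the documents. The exposed set is probably small and the effect could be close to zero, so putting a figure on the shift in incidence would be guesswork.

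The conclusion rests on three assumptions: that the investigator learns the arm when the code is broken, which is inferred; that no gating rule sits in a document not available here; and that the Medical Advisor's adjudication is not known to be blinded. The change is a cheap improvement worth making, not a flaw that threatens the trial's main conclusion.

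**What to change.** - **13.5, Table 4 and 13.8:** require every Stage 1 adverse event, including those from the Site Visit 2 interview, to be entered with severity and causality and signed by the investigator before that participant's code is released. Except emergency unblinding, and flag events rated after it. Gating on code release also settles the uncertainty over when Stage 1 ends.
- **16.6 and the SAP:** state that the Stage 1 table of related events uses the pre-disclosure rating, and list later changes to causality separately.
- **15.5:** state that the Medical Advisor adjudicates Stage 1 events blinded to allocation.

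The cost is one gating rule in the data capture system, a line in Table 4, short additions to 13.8, 15.5, 16.6 and the SAP, and a few minutes of data entry before disclosure at each Site Visit 2.

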10.3 Study Design Description

The study has two consecutive stages:

Stage 1 is a prospective, multi-centre, randomized, double-blind, sham-controlled, parallel-group, group-sequential study. The RCT design has been chosen to obtain high quality clinical data.

Stage 2 is an open-label extension with the active device (i.e. irrespective of the type of device (active/sham) used in Stage 1). At the start of Stage 2 the participant receives five devices for home use. This stage is included to provide more data on the consistency of the treatment response.

Each study participant will have two site visits:

- Site Visit 1 which is the screening/inclusion visit at which the participant starts their participation in Stage 1 (the randomized, controlled part of the study)
- Site Visit 2 which is the end of Stage 1 and start of Stage 2 (open-label extension)

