12.1.2 Exclusion criteria

Participants must meet none of the following criteria:

- 1. Participant has a history of chronic pulmonary disease (e.g. Chronic Obstructive Pulmonary Disease (COPD) or pulmonary fibrosis).
- 2. Participant has a history of severe cardiovascular disease (e.g. symptomatic coronary artery disease, prior myocardial infarction, congestive heart failure) or cerebrovascular disease (e.g. prior stroke or transient ischemic attack, symptomatic carotid artery disease, prior carotid endarterectomy or other vascular neck surgery).
- 3. Participant has a history of intracranial hyper/hypo-tension.
- 4. Participant has a history of cerebral aneurysm.
- 5. Participant has had previous brain surgery, including stenting.
- 6. Anaemia, defined as a hemoglobin concentration in capillary blood lower than 11 g/dL
- 7. Participant has a baseline S_{PO2} level which is lower than 95%
- 8. Participant has 15 or more headache days per month
- 9. Participant has medication-overuse headache (ICHD3 classification 8.2).
- 10. Participant has a known history or suspicion of recurring secondary headache which in the opinion of the investigator may interfere with the study.
- 11. Hemiplegic migraine
- 12. Participant has other significant and relevant pain problem (e.g. cancer pain, fibromyalgia or other head or facial pain disorders)
- 13. Participant has a known history or suspicion of substance abuse or addiction (within the last 5 years) that in the opinion of the investigator may confound the study assessments.
- 14. Participant has a history of psychiatric or cognitive disorder and/or behavioural problems which in the opinion of the investigator may interfere with the study.
- 15. Participant belongs to a vulnerable population or has any condition such that his or her ability to provide informed consent, comply with the follow-up requirements, or provide self-assessments is compromised (e.g. homeless, developmentally disabled, prisoner).
- 16. For female participants: is pregnant or actively trying to become pregnant.
- 17. Participant is participating in any other clinical investigation or has participated in an interventional clinical trial in the preceding 30 days.
- 18. Participant has any condition that according to the investigator may pose the participant at risk or provide confounding data.
- 19. Participant is unable, as perceived by study personnel, to correctly understand and follow the instructions for use of the device and ePRO app.

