- 20. Sickle Cell Disease
- 21. Participant is being treated with nerve blocks or injections for migraine prophylaxis on a regularly scheduled basis (including Botox, Aimovig/Erenumab, Ajovy/Fremanezumab, Emgality/Galcanezumab or Vyepti/Eptinezumab).

13 Study procedures

Figure 11 below shows the flow chart for the study and Table 2 lists the schedule of events.

[figure not shown]

Figure 11

PAREMA1 Clinical Investigation Plan version 3.6

	Site Visit 1 (screening / inclusion)	At-home training session	Follow-up A	Follow-up B	Follow-up C	Site Visit 2	End-of-Stage- 2 follow-up
Type of participant contact	Site visit	Tele- conference with instructor	Phone or tele- conference	Phone or tele- conference	Phone or tele- conference	Site visit	Phone or tele- conference
Time point	As soon as possible after successful online pre- screening or site identification	Maximally one week after randomizatio n	Maximally one week after first reported attack	Within one week if the participant has not registered an attack in the past eight weeks	Maximally one week after 4 reported attacks	Maximally two weeks after Follow- up C	Maximally two weeks after participant has used all Stage 2 devices or 12 months after Site Visit 2
Procedures:							
Informed Consent	Х						
Medical History	Х						
Pulse oximeter test	х						
Anaemia test	Х						
Pregnancy test (if applicable)	Х						
Migraine ACT questionnaire (part of CRF)	Х						
DASS-21 questionnaire (part of CRF)	Х					Х	
Medical history and migraine characteristics	Х						
Eligibility evaluation	Х						
Randomization	Х						
ePRO/safety and DD training	Х		Х	Х	Х	Х	
Device and ePRO training		Х					
Device dispensing	Х					Х	
Device return						Х	X (by mail)
Reimbursement of participant's costs						Х	
AE/SAE/DD reporting			Х	X X X		Х	Х
Deviation reporting	х		х	х	х	х	Х

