13.2.1 Informed Consent

The potential participant is briefed by the PI or delegated study personnel (hereafter designated PI) about the study, including the study rationale, study plan, randomization to either study device or sham device, study design and possible side effects of the treatment. It is clearly explained to the patient that they may be assigned to either a functional (active) or non-functional (sham) device in Stage 1, that it is believed that the active device has the best treatment effect and that the participant is guaranteed to be assigned to this in Stage 2.

If the participant wishes, he/she can have up to a week to consider before deciding whether or not to participate (in that case, the visit will be stopped after Step 1 and resumed when the participant has decided).

A potential study participant considered for this study must be listed on a screening log to be maintained at the site. The PI must also enter in the participant's medical records that he/she is participating in the study. If the participant does not have a medical record at the study site, a new record must be started for him/her.

PI will instruct female participants of childbearing potential to practice effective contraception during their participation in the study.

13.2.2 Information to be recorded:

The following information is obtained and documented in the eCRF during Site Visit 1 (cf. document **PAREMA1 Case Report Form content**):

- General eligibility questions (e.g. age, headache frequency, current participation in other clinical investigations)
- Eligibility questions related to migraine with aura diagnosis (presence of aura symptoms, frequency of MA attacks, age at MA onset)
- Eligibility questions related to headache drug use and overuse
- Eligibility questions related to comorbidities (e.g. pulmonary, cardiovascular and cerebrovascular disease)
- Eligibility questions related to secondary headaches (e.g. caused by head/neck trauma or infection)
- Pulse oximeter test result (see section 13.2.3)
- Capillary blood test for anaemia
- For female patients:
 - Whether the patient has gone through menopause
 - \circ $\;$ If patient has not gone through menopause: urine pregnancy test $\;$
- Other eligibility questions, including participant's willingness to abide by study instructions, and ability and willingness to provide informed consent.
- Migraine without aura (MO) diagnosis and frequency

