Apart from CO_2 effects, the risk assessment must also address the issue of possible hypoxemia. Any partial rebreathing device without an external source of compressed oxygen gas will inevitably lead to a decrease in the inspired oxygen level. However, individuals conforming to the in/exclusion criteria (i.e. without pulmonary or cardiovascular disease or anaemia) have a significant extra-capacity for oxygen uptake, meaning that decreases in the inspired oxygen pressure from the normal sea level value of 21 kPa (dry basis) down to 16 kPa are unproblematic and do not lead to hypoxemia (West, 2008). This corresponds to the situation which arises when a person travels from sea level to a high altitude. Signs of oxygen inadequacies upon exertion typically do not manifest themselves below altitudes of approx. 2200 meters, where the oxygen partial pressure is 16 kPa. In the present case, where the device users will be sitting at rest while using the device, the potential for hypoxemia is even smaller. This is supported by the arterial blood data which showed a drop of C_{aO2} of less than 2%, as well as the pulse oximetry data showing that the $S_{pO2\%}$ range was the same (95%-100%) with the study device as at baseline (see section 8.5.1).

Use of the Rehaler is contraindicated for the following:

- Chronic pulmonary disease (e.g. Chronic Obstructive Pulmonary Disease (COPD) or pulmonary fibrosis)
- Severe cardiovascular disease (e.g. symptomatic coronary artery disease, prior myocardial infarction, congestive heart failure (CHF)
- Cerebrovascular disease (e.g. prior stroke or transient ischemic attack, symptomatic carotid artery disease, prior carotid endarterectomy or other vascular neck surgery)
- Anaemia
- Sickle Cell Disease
- Uncontrolled intracranial hyper/hypo-tension
- Past or present cerebral aneurysm
- Individuals with previous brain surgery, including stenting
- Use in airplanes or at altitude over 2000 meters (6600 feet) above sea level
- Pregnant or breastfeeding women
- Children under the age of 18

Rehaler has potential interactions when used in conjunction with the following pharmaceutical agents:

1. Anesthetic agents: interaction can give rise to cardiac dysrhythmias.

- 2. Neuromuscular blocking agents and hypotensive agents: the change in pH induced by Rehaler can influence uptake, distribution and action of drugs (including neuromuscular blocking agents, and hypotensive anesthetic agents).

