14.3 Benefit-Risk Analysis

Section 14.1 describes possible adverse device effects and risks pertaining to the clinical investigation. Based on that analysis, we believe that it is unlikely that the use of the investigational device or sham device will lead to serious adverse device effects.

As detailed in the Risk Management file and summarized in the Investigator's Brochure, relevant measures have been taken to mitigate residual risks.

Based on the data from the scientific literature, prior clinical studies of functionally equivalent versions of the device (the studies CapnoMigra, HVMASKE and EpiCapno), the extensive post-market safety data, and the mitigations applied to residual risks, we believe it will be safe to use the investigational device and the sham device in the clinical investigation, in the population defined by the in/exclusion criteria.

The study is intended to examine in a large-scale, randomized, controlled study whether it is possible to treat and prevent migraine with aura by using partial rebreathing. Such a study has not previously been reported in the literature and will provide valuable new knowledge about migraine and its treatment. In the light of the risk evaluation performed, it is our assessment that those potential benefits of the study outweigh the risks and possible discomforts that participants may experience during the study, and that the benefit-risk ratio of the clinical investigation is therefore acceptable.

Our group (sponsor and investigators) possesses the required expertise, experience, equipment and facilities to carry out the proposed study, as well as subsequently analyze and communicate the results in a peer-reviewed journal.

15 Adverse events and device deficiencies

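### No pregnancy or contraindication re-check is scheduled at Site Visit 2 before active devices are dispensed for Stage 2, the sham arm's first active exposure

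*Protocol*

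**What the plan says.** **Entry.** Exclusion criterion 16 (protocol 12.1.2) reads "For female participants: is pregnant or actively trying to become pregnant". Protocol 13.2.2 puts the check at Site Visit 1: "If patient has not gone through menopause: urine pregnancy test".

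**Schedule.** In Table 2 the row "Pregnancy test (if applicable") has a single mark, under Site Visit 1. The medical history and eligibility evaluation rows have the same pattern. Device dispensing is marked at Site Visits 1 and 2. Section 10.3 states: "Each study participant will have two site visits". All other follow-up is by phone or teleconference.

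**Site Visit 2.** Section 13.5 and Table 4 list an end-of-Stage-1 interview (satisfaction, side effects, unreported adverse events, DASS-21, blinding guess), disclosure of the Stage 1 device, device return, Stage 2 training and the kit. The only stated condition for the kit is this: "Participant receives Stage 2 study kit if he/she re-consents to participating in Stage 2". The kit holds five active devices whatever the Stage 1 arm. Under 13.4.2.3, participants who at the end of Stage 1 "have not reported at least one study attack will be concluded from Stage 1 and invited to participate in Stage 2".

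**Safety basis.** The contraindications in 14.1.1 include "Pregnant or breastfeeding women". The benefit-risk conclusion in 14.3 is that use is safe "in the clinical investigation, in the population defined by the in/exclusion criteria".

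**The concern.** The protocol does not rely on contraception alone before Stage 1 dispensing: it also requires a urine test. Half of the women tested then receive a sham device, which by 14.1.2 gives less than 0.1% inspired CO2. When those women are handed the active device (1.5 to 2.5% inspired CO2) at Site Visit 2, no test or repeat of the contraindication questions is scheduled.

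Breastfeeding has a wider gap. It is a contraindication in 14.1.1 but is not named in 12.1.2, so neither visit has a named check for it. Only the investigator-judgement criterion (number 18) could cover it.

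A sham participant who became pregnant or began breastfeeding after Site Visit 1 could therefore receive a device that is contraindicated for her while everyone follows the plan as written.

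**Working it through.** No sample size, power or alpha figure is involved. The check compares the tables and then asks how old the entry screen is at Stage 2 dispensing.

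**1. What is scheduled**

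| Item | Site Visit 1 | Site Visit 2 |
|---|---|---|
| Medical history | yes | no |
| Pregnancy test | yes | no |
| Eligibility evaluation | yes | no |
| Device dispensing | yes (active or sham) | yes (active for all) |

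Section 13.4 has each participant use one device type throughout Stage 1, so sham participants have had no active exposure in the study before Site Visit 2.

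**2. Age of the screen, typical case.** Inclusion criterion 2 requires at least 3 attacks in six months, which is 0.5 per month. Stage 1 ends for a participant at four treated and reported attacks: 4 / 0.5 = 8 months if every attack is treated and reported, and less at higher rates.

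**3. Age of the screen, protocol maximum.** Section 10.3.1 gives at most 27 months in total and 12 months in Stage 2: 27 − 12 = 15 months.

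**4. Age of the screen, planned dates.** Participants who never reach four attacks stay until Stage 1 closes. From Q1 2023 to Q4 2025 this is 30.1 months (31 March 2023 to 1 October 2025) to 36.0 months (1 January 2023 to 31 December 2025) for the earliest enrolled. To see how often that could happen, assume Poisson attacks and no withdrawal. The chance of still being below four attacks at time *t* is P(Poisson(rate × *t*) ≤ 3):

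| Treated and reported attacks per month | 15 months | 30.1 months | 36 months |
|---|---|---|---|
| 0.5 (minimum entry rate) | 5.9% | 0.02% | 0.002% |
| 0.2 (assumed low rate) | 65% | 15% | 7% |

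Now average over uniform enrolment, with time to Stage 1 closure running from 6 to 6 + W months and W = 24.0 or 29.9 (31 March 2023 to 1 April 2025, or 1 January 2023 to 30 June 2025). The share below four attacks at closure is 9 to 11% at 0.5 per month and 45 to 54% at 0.2. Mean screen age in those groups is about 9.5 and 15 months. Of those below four, the share with a screen at least 30 months old is under 0.02% at 0.5 per month and at most 4.7% at 0.2.

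The SAP's planning split (1.5.1) is one third each with one, two and three study attacks. Adding the training attack, 1/3 + 1/3 = 2/3 of contributors would fall short of four, a larger share than the model gives. The SAP also plans 22% dropout, which the model omits. The share is therefore not fixed by the documents.

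**5. Number of people.** Sham participants randomised 1:1 number 174/2 = 87 to 220/2 = 110 under the protocol, or 200/2 = 100 to 240/2 = 120 under the SAP. Each 1% is 0.87 to 1.2 people. The share who re-consent, and the share who are women before menopause, are not given.

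**The case against.** The strongest reply is that several safeguards already operate:

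- Contraception is an inclusion criterion and covers the whole of participation.
- Follow-up B obliges the investigator to contact anyone with no attack registered in eight weeks, and Table 2 marks adverse event reporting at Follow-ups A, B and C. Participants with an old screen are therefore not out of contact.
- Site Visit 2 has an interview, device and safety training, and a re-consent that need not be a bare signature, since 20.4 requires information on device and risks.
- Conditions for use are in the verbal and written instructions, the IFU and the kit label (8.2), and the investigator may withdraw a participant (19.5).

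This stands as far as overt diagnoses go. It does not supply a scheduled step for a pregnancy that is unrecognised or unreported, or for breastfeeding, which is not an adverse event.

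A reader might infer that screens three years old are common. The documents do not support that: the 30 to 36 month figure is a rare tail. Screen age also says little about a current pregnancy once it passes about nine months.

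A reader might also infer that the protocol contradicts itself or leaves participants unprotected. It does neither. It relies on contraception and instructions after entry, also for the active arm during Stage 1. A single test at dispensing would not cover a pregnancy later in Stage 2, which can last 12 months.

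Finally, the Case Report Form content document, the IFU and the consent form were not available. Any of them may contain the missing question.

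**Conclusion.** The point holds as a cheap improvement to participant safety. As scheduled, five active devices go to every participant who re-consents, and nothing in the two documents is designed to find pregnancy or breastfeeding first. It matters most for the sham arm; active-arm participants have already used the device.

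The screen is about 8 months old at the minimum entry rate if all attacks are treated and reported, and up to 15 months old on the protocol's stated maximum. Gaps beyond 15 months are uncommon at the minimum entry rate. They become frequent only if reported attacks fall well below it, which is an assumption. The number of participants with a new contraindication is unknown and probably small.

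It would be wrong to infer any effect on the trial's results. Section 11 takes all primary and secondary effectiveness endpoints from Stage 1.

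**What to change.** In Tables 2 and 4, before Stage 2 dispensing at Site Visit 2, add:

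1. A re-ask of the 14.1.1 contraindications, with breastfeeding named.
2. A repeat urine pregnancy test in women who have not gone through menopause.
3. A rule that the Stage 2 kit is dispensed only if no contraindication is found.

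Contraception remains the safeguard after that visit. If the Case Report Form already asks these questions, showing them in the two tables is enough for item 1.

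The cost is a few minutes and one urine test at a visit that already takes place, plus the table entries. The downside is that a few participants may not enter Stage 2.
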